10.1.1 SAFETY ANALYSES

Safety will be assessed by wound examination, clinical laboratory tests and collection of AEs as outlined in the Schedule of Events. All summaries of AEs will be based on treatment-emergent AEs and presented using the incidence and a tabulation of the number of events. The number and percentage of subjects experiencing AEs will be summarized by system organ class and description. Summaries by maximum severity and relationship to the study treatment will also be provided. SAEs and AEs leading to discontinuation from the study will be presented by system organ class and preferred term.

10.1.2 PLANNED INTERIM ANALYSES

There are no planned interim analyses for this clinical investigation.

10.2 SAMPLE SIZE

Estimated 80 subjects will be treated (maximum of 100) in this prospective cohort evaluation of all wounds that will be managed with ACell, Inc. Urinary Bladder Matrix products.

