	
debridement, offloading, negative pressure wound therapy, hyperbaric oxygen).
 
4. Number and type of wound-related adverse events through week 12 as recorded on adverse event case report forms.
 
Tertiary Endpoints
 
1. Costs of treatment and patient work status through week 12 will be assessed by the following:
 
 a. Direct wound-related costs will be calculated and stratified by product and care cost. b. Current employment status and return to work status will be recorded and frequency of changes will be assessed. c. Measure frequency of wound specific AEs, and SAEs. 
2. Wound Pathology will be assessed through week 12 by the following:
 
 a. Effect of treatment with Cytal® with or without MicroMatrix® on pro-inflammatory and anti-inflammatory macrophage biomarkers, vascularization, and fibrosis in wound tissue biopsies will be assessed through quantitative image analysis for the following stains: 
 i. CD86 and CD163 immunostains to quantify pro-inflammatory M1 and anti-inflammatory M2 macrophage phenotypes. ii. CD31 immunostain to quantify vascularization. iii. Masson’s trichrome to quantify fibrosis. b. Pathologists’ findings over the course of treatment will be assessed by quantification of standardized pathologists’ findings in wound pathology reports based on Hematoxylin and Eosin staining.

Number of Subjects:
	
Estimated 80 subjects for treatment. (Maximum of 100). Subjects who are screened and meet all eligibility are enrolled in the study.

Study Criteria:
	
Inclusion Criteria: (All inclusion criteria must be met for enrollment)
 
 1. Subject has at least one wound that the treating physician determines may be treated with Cytal® with or without MicroMatrix®. 2. Subject is ≥ 22 years of age.

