	
 3. Subject is willing and able to adhere to protocol requirements and agrees to participate in the study program and comply with the study follow-up regimen. 4. Subject or legal representative is willing to provide informed consent. 5. For females of reproductive potential, confirmed negative pregnancy test at enrollment. 
Exclusion Criteria: (No exclusion criteria may meet for enrollment)
 
 1. Allergy or hypersensitivity to materials in porcine-based study products (per subject report) or personal preference. 2. Subject report of concurrent participation in another clinical trial that involves an investigational drug or device that would interfere with this study. 3. The subject has any physical or psychiatric condition that, in the Investigator's opinion, would warrant exclusion from the study or prevent the subject from completing the study. 4. The subject's wound shows evidence of infection as determined by the Principal Investigator (which may be indicated by presence of: elevated WBC, pus, moderate or greater discharge, abnormal odor, or acute osteomyelitis). 5. Wound with exposed organs or hardware. 6. Wound with burn etiology.
Number of Sites enrolling participants:	1 (NYU Winthrop Hospital)
ACell Study Products:	
 1. Cytal®™ Wound Matrix 1-Layer 2. MicroMatrix®
Participant & Study Duration:	
80 subjects are expected to complete this trial (maximum of 100 may be enrolled). The duration of participation for each subject will be up to a maximum of 55 weeks (1 week screening/treatment; 12 week follow-up; 26 week confirmation of wound closure/recurrence; 52 week final study visit). All visits have protocol stipulated windows.
 
Recruitment and enrollment efforts are expected to last for approximately 12 months, starting in June 2018. The study will end in approximately May 2019, with Last Subject Last Visit expected in May 2020.
 
The actual overall study duration or subject recruitment period may vary.

Statistical Methodology:	The objective of this study is to define the trajectory of healing using either 1 or 2 test products; the intra-patient change will be the focus

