5.3 STRATEGIES FOR RECRUITMENT AND RETENTION

80 subjects (maximum of 100 enrolled) are expected to complete the trial after an approximate 20% dropout/withdrawal rate. The enrollment process will take place over a 12 month period

between June 2018 and May 2019, with all subjects expected to have completed the study by May 2020. All eligible patients will be selected for participation from within NYU Winthrop Hospital, including the outpatient Wound Healing Center clinic.

Patients will be compensated for participation in the trial. Patients will receive one \$25 gift card for each study visit (1 – 12), as well as a \$50 gift card for both the Long-Term Follow-Up visit at Week 26 and the Final Study visit at Week 52.

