5.4.2 HANDLING OF PARTICIPANT WITHDRAWALS OR TERMINATION

Although subjects may withdraw from the study at any time and for any reason, (or may be withdrawn at the Investigator's discretion), subject withdrawal should be avoided as much as reasonably possible. However, data already accumulated on the patient will be utilized in the final analysis.

Subjects who prematurely discontinue are not to be replaced. For subjects considered lost to follow-up, the CRFs must be completed up to the last visit performed.

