5	64.06	75.00	84.01

For mean changes from baseline, if the standard deviation of the difference from baseline for a parameter is 10 units, the confidence level will exceed 90% with a distance from the mean to the limit as small as 2 units.

For data derived from a binomial distribution and a continuous distribution, 80 patients should be sufficient to detect a clinically-meaningful change in this clinical investigation.

In summary, the sample size for this clinical investigation is sufficient to detect a 34% difference in the proportion of responders between the 2 treatments (power: 81.9%, alpha: 5%, 40 patients per treatment arm with 30% response and 64% response, respectively). If the observed proportion of response between the 2 treatment arms is 15% and 46% respectively, with 40 patients per treatment arm, the power will be 81.1%. If there is an imbalance between the 2 treatment arms (30 patients and 50 patients, respectively), and observed proportion of response between the 2 treatment arms is 15% and 47%, the power will be 80.3%.

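### The sample size is stated as both 80 treated and 80 completing after about 20% loss, and the 80-patient precision table contains a row computed on 100

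*Combined protocol and SAP*

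**What the plan says.** Two places give 80 as the number treated. Section 10.2 reads "Estimated 80 subjects will be treated (maximum of 100", and the synopsis entry on number of subjects reads "Estimated 80 subjects for treatment. (Maximum of 100".

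Two places give 80 as the number finishing. The synopsis entry on participant and study duration reads "80 subjects are expected to complete this trial (maximum of 100 may be enrolled", and section 5.3 reads "80 subjects (maximum of 100 enrolled) are expected to complete the trial after an approximate 20% dropout/withdrawal rate".

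Two further statements bear on whether these can agree. Section 5.4.2 says "Subjects who prematurely discontinue are not to be replaced", and the synopsis defines enrolment: "Subjects who are screened and meet all eligibility are enrolled in the study".

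Section 10.1 then bases its precision statements on 80 patients. For proportions it puts the distance from the estimate to the 95% limit at 9% to 10%, with a five-row table of exact limits. For mean changes, with an SD of 10 units, it says that "the confidence level will exceed 90% with a distance from the mean to the limit as small as 2 units". The same section classifies a patient who withdraws by the last recorded observation (closed or not closed) and applies this rule to the percent-reduction thresholds as well.

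**The concern.** With 20% loss and no replacement, the number treated and the number completing cannot both be 80. A site working from section 10.2 could stop at 80 treated; one working from section 5.3 would continue towards 100. That is 25% more patients (100/80 = 1.25), depending on which section is read.

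The plan justifies its size by precision, so each precision figure needs a known n. The table suggests that both numbers were used in preparing it. Its 40% row spans 19.95 points, while the 37.5% row, further from 50%, spans 22.12. At one common n the 40% row should be the wider.

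**Working it through.** **1. Enrolment arithmetic.** Inputs: 80 and 100 (synopsis, 5.3, 10.2) and 20% loss (5.3).

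- If 80 complete: treated = 80/(1 − 0.20) = 100, which equals the stated maximum.
- If 80 are treated: completers = 80 × (1 − 0.20) = 64. The plan does not state this number anywhere.

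**2. The precision table.** Exact (Clopper-Pearson) limits for x responders of n: lower = Beta quantile 0.025 with parameters (x, n − x + 1); upper = Beta quantile 0.975 with parameters (x + 1, n − x).

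| Row | Response | Printed limits (%) | Exact at n = 80 | Exact at n = 100 |
|---|---|---|---|---|
| 1 | 25% | 15.99 to 35.94 | 20/80: 15.99 to 35.94 | 25/100: 16.88 to 34.66 |
| 2 | 37.5% | 26.92 to 49.04 | 30/80: 26.92 to 49.04 | not a whole number of patients |
| 3 | 40% | 30.33 to 50.28 | 32/80: 29.20 to 51.56 | 40/100: 30.33 to 50.28 |
| 4 | 62.5% | 50.96 to 73.08 | 50/80: 50.96 to 73.08 | not a whole number of patients |
| 5 | 75% | 64.06 to 84.01 | 60/80: 64.06 to 84.01 | 75/100: 65.34 to 83.12 |

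Rows 1, 2, 4 and 5 reproduce at n = 80. Row 3 reproduces at n = 100.

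**3. The 9% to 10% distance.** Distances from the estimate to each limit at n = 80:

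| Response | To lower limit | To upper limit |
|---|---|---|
| 25% | 9.01 | 10.94 |
| 37.5% | 10.58 | 11.54 |
| 40% | 10.80 | 11.56 |
| 62.5% | 11.54 | 10.58 |
| 75% | 10.94 | 9.01 |

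Only the shorter side at 25% and 75% lies between 9 and 10. The longer side runs from 10.94 to 11.56. The normal approximation, 1.96 × √(p(1 − p)/80), gives 9.49 at 25% and 75%, but 10.61 at 37.5% and 62.5% and 10.74 at 40%, so it does not rescue the statement. At n = 100 the longer exact side is 9.66 at 25% and 75% and 10.28 at 40%, which is much nearer to the claim.

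**4. Mean change.** Inputs: SD 10 and distance 2 (10.1). Confidence = 2Φ(2√n/10) − 1, or the same with the t distribution on n − 1 degrees of freedom.

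| n with a change value | Normal | t |
|---|---|---|
| 80 | 92.6% | 92.3% |
| 70 | 90.6% | 90.1% |
| 69 | 90.3% | 89.9% |
| 68 | 90.1% | 89.6% |
| 67 | 89.8% | 89.4% |
| 64 | 89.0% | 88.5% |

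The plan's figure reproduces at n = 80. It needs at least 68 (normal) or 70 (t) patients with a value. From 80 treated, that tolerates a loss of (80 − 68)/80 = 15% or (80 − 70)/80 = 12.5%. At n = 64 the 90% half-width would be 2.06 (normal) or 2.09 (t) rather than 2.

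**The case against.** **The numbers can be reconciled.** 100 × 0.80 = 80, so the cap may simply be the dropout allowance. That fits section 5.3 and the synopsis duration entry. It does not fit section 10.2 or the synopsis entry on number of subjects, which give 80 as the expected number treated and 100 as a ceiling. Another attempt is that 100 enrol, 20 leave before treatment, and 80 are treated and finish. This needs all the loss to fall between confirmed eligibility and first application, at most 7 days apart and possibly one visit. Screen failures cannot fill the gap, because only eligible subjects count as enrolled. Section 10.2 also attaches the 100 to treatment, not to enrolment.

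**The mean-change statement is not shown to fail.** A reader might infer that with 80 treated the 90% figure is missed, because 64 remain. This objection stands. The 20% comes from the sentence that takes 80 as completers. It concerns completing a trial that runs to week 52, whereas the change endpoints are assessed through week 12. Section 5.4.2 also says that data already collected will be used; wound area is measured weekly, and surveys are taken at week 6 and at healing. No imputation rule for continuous variables is given, so the loss is possible but not established. The SD of 10 is itself only illustrative, and the worst case misses by 1.0 to 1.5 points.

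**Completers do not set the precision of the primary endpoints.** A reader might infer that withdrawals widen those intervals. Section 10.1 keeps withdrawn patients in the denominator, so the relevant n is the number treated.

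**The distance error is a separate fault.** This is correct: it is present with no dropout. It belongs here because the same choice of n and the same recalculation correct it.

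**Conclusion.** The point holds for the stated sample size and for the proportion figures. The two sample size statements are incompatible at the plan's own 20% loss, and they differ by 20 treated patients. One of the five table rows is on the wrong n: at n = 80 its limits move from 30.33 and 50.28 to 29.20 and 51.56. The 9% to 10% statement understates the longer side by about 1 to 1.6 points at n = 80 (10.94 and 11.56 against an upper figure of 10). The table and distance findings need no assumption about dropout.

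The mean-change statement is correct for 80 evaluable patients. It would drop to 88.5% to 89.0% only if the full 20% loss fell on 80 treated before the week-12 value and those patients supplied no change score. The documents do not say that this will happen.

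This should be corrected because the plan relies on these figures, but the shortfalls in precision are small.

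**What to change.** 1. Use one basis in both synopsis entries, section 5.3 and section 10.2. One option is up to 100 treated with about 80 expected to complete, which lies within the existing cap. The other is 80 treated, with a correspondingly lower number expected to complete.
2. Recompute every table row and the distance statement at the number treated. At 80, row 3 becomes 29.20 to 51.56 and the longer-side distance 10.9 to 11.6 points. At 100, all rows change except row 3, and the 37.5% and 62.5% rows need response rates that correspond to whole patients.
3. State the mean-change precision for the number expected to be evaluable at week 12, with the assumed loss by that visit and how missing continuous values are handled. The note that 68 (normal) or 70 (t) evaluable patients are enough can be added.

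The cost is wording in the synopsis and sections 5.3, 10.1 and 10.2, plus a short recalculation. Choosing 100 treated makes the present ceiling the recruitment target. Keeping 80 treated means accepting a less favourable distance statement than the one now printed.

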11. SOURCE DOCUMENTS AND ACCESS TO SOURCE DATA/DOCUMENTS

Participating site will maintain appropriate medical and research records for this trial, in compliance with ICH E6 and regulatory and institutional requirements for the protection of confidentiality of participants. The site will permit authorized representatives of the Sponsor or designee, and regulatory agencies to examine (and when permitted by applicable law, to copy) clinical records for the purposes of quality assurance reviews, audits, and evaluation of the study safety, progress, and data validity.

Source data are all information, original records of clinical findings, observations, or other activities in a clinical trial necessary for the reconstruction and evaluation of the trial. Examples of these original documents and data records include, but are not limited to, hospital records, clinical and office charts, laboratory notes, memoranda, participants' memory aids or evaluation checklists, pharmacy records, recorded data from automated instruments, photographic negatives, and participant files and records kept at the pharmacy, at the laboratories, and medico-technical departments involved in the clinical trial.

12. QUALITY ASSURANCE AND QUALITY CONTROL

Quality Control (QC) procedures will be implemented beginning with the data entry system and data QC checks that will be run on the database. Any missing data or data anomalies will be communicated to the site for clarification/resolution.

Following written Standard Operating Procedures, the monitors will verify that the clinical trial is conducted and data are generated, documented (recorded), and reported in compliance with the protocol and GCP.

The site will provide direct access to all trial related materials, including source data/documents, electronic medical records (if applicable), CRFs, and reports for the purpose of monitoring and auditing by the Sponsor and/or the IRB.

13. ETHICS/PROTECTION OF HUMAN SUBJECTS

13.1 ETHICAL STANDARD

The Investigator will ensure that this study is conducted in full conformity with Regulations for the Protection of Human Subjects of Research codified in 45 CFR Part 46, 21 CFR Part 50, 21 CFR Part 56, and/or the ICH E6.

13.2 INSTITUTIONAL REVIEW BOARD

The protocol, informed consent form(s), and all participant materials will be submitted to the NYU Winthrop Hospital IRB for review and approval. Approval of both the protocol and the consent form must be obtained before any participant is enrolled. Any amendment to the protocol will require review and approval by the IRB before the changes are implemented to the

study. All changes to the consent form will be IRB approved; a determination will be made regarding whether previously consented participants need to be re-consented.

13.3 INFORMED CONSENT PROCESS

Informed consent is a process that is initiated prior to the individual's agreeing to participate in the study and continues throughout the individual's study participation. Extensive discussion of risks and possible benefits of participation will be provided to the participants and their families. Consent forms will be IRB approved and the participant will be asked to read and review the document. The Investigator will explain the research study to the participant and answer any questions that may arise. All participants will receive a verbal explanation in terms suited to their comprehension of the purposes, procedures, and potential risks of the study and of their rights as research participants. Participants will have the opportunity to carefully review the written consent form and ask questions prior to signing. The participants will have the opportunity to discuss the study with their surrogates or think about it prior to agreeing to participate. The participant will sign the informed consent document prior to any procedures being done specifically for the study. The participants may withdraw consent at any time throughout the course of the trial. A copy of the signed informed consent document will be given to the participants for their records. The rights and welfare of the participants will be protected by emphasizing to them that the quality of their medical care will not be adversely affected if they decline to participate in this study.

If a consent document is revised due to changes in study procedures, subjects who were enrolled prior to the change, but are affected by the change, will be informed of the changes and will sign the amended consent document. If a consent document is revised due to changes in the risks or safety of the study, all active participants must sign the revised consent and a signed copy will be given to them.

13.4 PARTICIPANT AND DATA CONFIDENTIALITY

Participant confidentiality is strictly held in trust by the participating Investigator(s), their staff, the Sponsor and their agents. The study protocol, documentation, data, and all other information generated will be held in strict confidence. No information concerning the study or the data will be released to any unauthorized third party without prior written approval of the Sponsor.

The study monitor, other authorized representatives of the Sponsor, and/or representatives of the IRB may inspect all documents and records required to be maintained by the Investigator for the participants in this study. The clinical study site will permit access to such records.

The study participant's contact information will be securely stored at the clinical site for internal use during the study. At the end of the study, all records will continue to be kept in a secure location for as long a period as dictated by the local IRB and Institutional regulations.

14. DATA HANDLING AND RECORD KEEPING

14.1 DATA COLLECTION AND MANAGEMENT RESPONSIBILITIES

Data collection is the responsibility of the clinical trial staff at the site under the supervision of the site PI. The investigator is responsible for ensuring the accuracy, completeness, legibility, and timeliness of the data reported.

All source documents should be completed in a neat, legible manner to ensure accurate interpretation of data. Black ink is required to ensure clarity of reproduced copies. When making changes or corrections, cross out the original entry with a single line, and initial and date the change. Do not erase, overwrite, or use correction fluid or tape on the original.

Copies of the electronic CRF (eCRF) will be provided for use as source documents and maintained for recording data for each participant enrolled in the study. Data reported in the eCRF derived from source documents should be consistent with the source documents or the discrepancies should be explained and captured in a progress note and maintained in the participant's official electronic study record.

Clinical data (including AEs, concomitant medications, and expected adverse reactions data) and clinical laboratory data will be entered into ACell's EDC system, a 21 CFR Part 11-compliant data capture system. The data system includes password protection and internal quality checks, such as automatic range checks, to identify data that appear inconsistent, incomplete, or inaccurate. Clinical data will be entered directly from the source documents.

14.2 STUDY RECORDS RETENTION

All study documents (patient files, signed informed consent forms, Study Regulatory Binder, etc.) must be kept secured for a period of two years following completion of the study. There may be other circumstances for which the Sponsor is required to maintain study records and, therefore, the Sponsor should be contacted prior to removing study records for any reason. It is the responsibility of the Sponsor to inform the Investigator when these documents no longer need to be retained.

14.3 PROTOCOL DEVIATIONS

A protocol deviation is any noncompliance with the clinical trial protocol or GCP requirements. The noncompliance may be either on the part of the participant, the Investigator, or the study site staff. As a result of deviations, corrective actions are to be developed by the site and implemented promptly.

All protocol deviations/violations should be documented using the Protocol Deviations CRF and submitted to the IRB according to their reporting guidelines.

14.4 PUBLICATION AND DATA SHARING POLICY

The preparation and submittal for publication of manuscripts containing the study results shall be in accordance with a process determined by mutual written agreement among the study Sponsor and participating institutions. The publication or presentation of any study results shall comply with all applicable privacy laws, including, but not limited to, the Health Insurance Portability and Accountability Act of 1996.

